## 1.3. Clinical Studies

Approximately 2000 volunteers have been challenged in studies conducted by [name], [name], [name], [name], and our other colleagues at UVA over the last 30 years and no serious complications attributable to the viral infection have been detected. The clinical syndrome associated with experimental infection is well-described. Challenge of volunteers with 100 TCID50 produces infection in 90-95% of susceptible volunteers. Symptoms first appear within 24 hours after inoculation and peak at 48-72 hours after challenge. The clinical syndrome is comparable to that reported in natural colds (52, 53) although in one study with identical definitions for duration, the median duration of illness was 3.5 days in volunteers with experimental colds and 5.5 days in volunteers with natural colds (54). Approximately 1/3rd of RV infections, whether natural or experimental, are asymptomatic. Virus shedding in infected volunteers follows a pattern similar to that of the symptoms. Virus concentrations in nasal lavage fluid, based on titers in culture, generally peak 2-3 days after challenge and then rapidly decrease. Virus can still be recovered by culture in 20% of subjects on day 18 after challenge, but no virus shedding is detected by day 20 (55). To the best of our knowledge, human RV-16 has not been withdrawn from investigation or marketing in any country for any reason related to safety or effectiveness. In our studies, we have observed neutropenia in most of the 29 asthmatic subjects and also 16 controls following inoculation with RV-16 in our experimental challenges, which we believe is in keeping with the recruitment of neutrophils into the airways stimulated by RV. However, except for the possibility of bronchitis, which occurs infrequently in experimental infections, no subject has developed clinically significant bacterial infections in our studies, including bacterial sinusitis. Additionally, no subject in our studies with RV-16 has developed ANC's <1000 cells/mm^3.

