## 5. Known and Potential Risks and Benefits to Participants

### 5.1. Risks of Investigational Product or Intervention

Approximately 2000 volunteers have been challenged in studies conducted by [name], [name], [name], [name], and their colleagues over the last 30 years and no serious complications attributable to the viral infection have been detected. The clinical syndrome associated with experimental infection is well described. Challenge of volunteers with approximately 300 TCID50 of RV produces infection in 90 to 95% of susceptible volunteers. Symptoms first appear within 24 hours after inoculation and peak at 48-72 hours after challenge. The clinical syndrome is comparable to that reported in natural colds (52, 53). Approximately one-third of RV infections, whether natural or experimental, are asymptomatic. Virus shedding in infected volunteers follows a pattern similar to that of the symptoms. Virus concentrations in nasal lavage fluid, based on titers in culture, generally peak 2-3 days after challenge and then rapidly decrease. Virus can be recovered by culture in 20% of subjects on day 18 after challenge, but no virus shedding is detected by day 20 (55). To the best of our knowledge, human RV-16 has not been withdrawn from investigation or marketing in any country for any reason related to safety or effectiveness. In our studies, we have observed neutropenia in most of the 29 asthmatic subjects and also 16 controls following inoculation with RV-16 in our experimental challenges, which we believe is in keeping with the recruitment of neutrophils into the airways stimulated

by RV. However, except for the possibility of bronchitis, which occurs infrequently in experimental infections, no subject has developed clinically significant bacterial infections in our studies, including bacterial sinusitis. Additionally, no subject in our studies with RV-16 has developed ANC's less than 1000 cells/mm^3. Should any subject develop an ANC or ALC below 500/ $\mu$ L on Day 4, a repeat CBC will be done on Day 14 to ensure that the value has returned to baseline or into the normal range, whichever is lower. If the value has not recovered at on Day 14, another CBC will be completed on Day 21. If the value remains low following the Day 21 draw, the subject will be referred to his or her regular healthcare provider for follow-up.

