**Study therapy regimen:**

- Rhinovirus-16 administration  
Rhinovirus infection is expected to result in cold symptoms among all subjects, and mild asthma symptoms among the asthmatic cohort. In addition, neutropenia and lymphopenia are expected within the first week after rhinovirus inoculation without clinical consequence. Upper and lower respiratory symptom data will be recorded on the RV Dairy Symptom Cards completed by study participants. An adverse event will be recorded in the following circumstances –
  - Treatment with an antibiotic or inhaled or systemic corticosteroid
  - Drop in lung function to  $\leq 70\%$  of predicted or ACT score  $< 19$
  - Febrile Neutropenia (ANC  $< 1000/\mu\text{L}$  with a single temperature of  $> 38.3$  degrees C (101 degrees F) or a sustained temperature of  $\geq 38$  degrees C (100.4 degrees F) for more than one hour)
  - Lymphopenia (ALC  $< 800/\mu\text{L}$ )
  - Any cytopenia with appropriate associated symptoms

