**12.2.3 Unexpected Adverse Event**

An adverse event or suspected adverse reaction is considered “unexpected” if it is not consistent with the risk information described in the Investigational Brochure.

Expected Risks related to Rhinovirus-16 inoculation and infection:	Frequency

 
• A decline in absolute blood neutrophil counts within first week following inoculation
 
• Bacterial sinus infection
 
• Lower respiratory tract infection (bronchitis)
 
• Lymphopenia within first week following inoculation
 
	
 
• Occurs frequently, but not known to be clinically significant.
 
• Occurs infrequently.
 
• Occurs infrequently. Rhinovirus is not known to cause pneumonia.
 
• Occurs infrequently, and not known to be clinically significant
 

 
• Cold symptoms could cause severe wheezing and shortness of breath, requiring additional; treatment
 
	
 
• Occurs infrequently
 

Expected Risks related to Spirometry Testing (excluding use of Methacholine)	Frequency

 
• Mild light-headedness and coughing
 
	
 
• Occurs frequently,
 

 
• Chest soreness
 
• Mild respiratory fatigue
 
• Mild shortness of breath
 
• Chest Tightness
 
• Fainting
 
	
 
• Occurs rarely
 

Expected Risks related to use of Methacholine	Frequency

 
• Mild asthma symptoms
 
	
 
• Occurs frequently,
 

 
• Coughing
 
• Fainting
 
• Chest tightness
 
• Shortness of breath
 
• Wheezing
 
	
 
• Occurs infrequently
 

 
• Bronchoconstriction
 
	
 
• Occurs frequently
 

Expected Risks related to Albuterol (if needed following Methacholine testing)	Frequency

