## 13. Statistical Considerations and Analytical Plan

### 13.1 Overview

**Objectives:** Our primary objective will be to address the hypothesis that epigenetic changes selectively develop in nasal epithelial cells (EC) during the evolution of allergic airway disease as a result of which nasal EC are programmed to produce cytokines central to orchestrating an allergic inflammatory immune response in the upper – and lower – airways. We will determine whether nasal epithelium from allergic asthmatics and rhinitics when infected with RV, is programmed to secrete cytokines that promote a Th2 cytokine “signature” (IL-25, IL-33, and TSLP) as well as mediators directly driving engagement of an allergic inflammatory process (including CCL5, CCL11, CXCL1, and GMCSF). A total of 60 subjects will be enrolled including 20 each that are normal controls, allergic rhinitis controls, and asthmatics. Cytokine/chemokine will be collected at day 0, 1, 2, 3, 4, and 7 post-infection and evaluated by qPCR and EIA.

We will correlate the expression of these cytokines with engagement of an allergic inflammatory response, including eosinophil co-recruitment at days 1-4. In addition, we predict that in asthma and AR systemic increases in eosinophilia will be observed, but that only in asthmatics will increased asthma symptoms, bronchial hyperreactivity, and eNO be observed.

**Analytical approach:** The RV challenge model is an example of a serial study design, in which subjects will receive a nasal presentation of RV-16 on challenge day 0 and then they will be serially monitored in the CRU for 7 days. **Analytical method selection:** Due to the fact that most of our data collection will be serial in nature, i.e. data will be collected on challenge days 0, 1, 2, 3, 4, and 7, the analytical methods that we select to use to analyze our primary and secondary outcome data will take into account the *repeated measure* aspect of the RV challenge model. **Missing data:** We will make a concrete effort to limit the occurrence of missing data, and if deemed necessary, multiple-imputation methods will be utilized to control biases associated with incomplete data. **Levels of detection:** If specimen levels are below the level of assay detection, we will use the mid-point between 0 and the minimum detection level of the assay as the unit of analysis.

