***Analysis of circulating eosinophil count:*** Changes in the absolute eosinophil count (AEC) from day -7 to post-challenge day 4 will be compared between the 3 different groups via ANOVA. ***Model specification:*** The primary source of  $\Delta$  AEC variation that will be examined will be the variation due to study-group to study-group variation. ***Hypothesis testing:*** We will test if the 3 underlying study-population  $\Delta$  AEC distributions share the same mean. A  $p \leq 0.05$  decision rule will be utilized as the null hypothesis rejection rule for this test. If rejected a Bonferroni corrected two-sided  $p \leq 0.05/3$  decision rule will be utilized as the null hypothesis rejection rule for between-group comparisons. ***Alternative analytical approach:*** If the ANOVA model assumptions are violated, the  $\Delta$  %EC data will be analyzed by *distribution-free* permutation methods.

***Analysis of eosinophil percent of total cells:*** Changes in the eosinophil percent of total cells ( $\Delta$  %EC) from day -7 to post-challenge day 4 will be compared between the 3 different groups via ANOVA. ***Model specification:*** The primary source of  $\Delta$  %EC variation that will be examined will be the variation due to study-group to study-group variation. ***Hypothesis testing:*** We will test if the 3 underlying study-population  $\Delta$  %EC distributions share the same mean. A  $p \leq 0.05$  decision rule will be utilized as the null hypothesis rejection rule for this test. If rejected a Bonferroni corrected two-sided  $p \leq 0.05/3$  decision rule will be utilized as the null hypothesis rejection rule for between-group comparisons. ***Alternative analytical approach:*** If the ANOVA model assumptions are violated, the  $\Delta$  %EC data will be analyzed by *distribution-free* permutation methods.

***Analysis of upper respiratory symptom scores:*** The upper respiratory symptom scores that will be reported daily from challenge study day 0 to challenge study day 7, will be analyzed in two ways. In the first approach, cumulative upper respiratory total symptom (CURTS) will be computed for challenge days 0 to 4, and for challenge days 0 to 7. In the second approach the daily total upper respiratory symptom scores will be analyzed. *Please see the analytical plan for the analysis lower respiratory symptom scores for further details (section 13.4.2).*

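### The fallback analysis for the absolute eosinophil count names the change in eosinophil percent instead, a measure that moves with neutrophils even when eosinophils do not

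*Combined protocol and SAP*

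**What the plan says.** Section 13.4.4 has two adjacent paragraphs on eosinophils.

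- **AEC.** The change from day -7 to day 4 is compared across the three cohorts by ANOVA. The 0.05 "decision rule will be utilized as the null hypothesis rejection rule for this test", and pairwise tests follow at 0.05/3. If the ANOVA assumptions are violated, the paragraph turns to the Δ% measure: "EC data will be analyzed by *distribution-free* permutation methods".
- **Percent.** "Changes in the eosinophil percent of total cells" over the same days are analysed in the same way, and the paragraph closes with the same fallback sentence. There is no term for baseline percent, neutrophils or total count.

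The specimen is not named in the percent paragraph. Table I starts nasal sampling on day 0 and takes blood for AEC on days -7 and 4, so the percent must come from the blood differential.

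Only the absolute count is a listed secondary endpoint (synopsis, Secondary Endpoints item 4; Section 3.2 item 4; Section 13.2). Eosinophil percent is in none of these lists.

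On neutrophils, Sections 1.3 and 5.1 report that "we have observed neutropenia in most of the 29 asthmatic subjects and also 16 controls following inoculation with RV-16". Section 12.2.1 says "neutropenia and lymphopenia are expected within the first week after rhinovirus inoculation without clinical consequence". Section 12.2.3 lists "A decline in absolute blood neutrophil counts within first week following inoculation" as frequent. Section 1.1 points the other way: it cites published work showing neutrophilia after experimental RV.

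Section 13.1 predicts that "in asthma and AR systemic increases in eosinophilia will be observed".

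**The concern.** Taken literally, the AEC paragraph has no fallback for AEC. If the ANOVA is set aside, what is tested next is a different variable.

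The fallback could well be needed. Section 13.4.4 specifies no transformation for AEC, whereas Sections 13.4.2 and 13.4.4 provide for one for IL-25, FEV1, FeNO and the interferons. Nor does the plan say how a violation is to be judged.

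The replacement measure depends on its denominator. If neutrophils fall by day 4, eosinophil percent rises although no eosinophil count has changed. Such a rise could be read as support for the Section 13.1 prediction when it reflects neutrophils only. A permutation test removes the reliance on normality. It does not remove this dependence, which is in the quantity being tested.

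**Working it through.** **Figures in the plan.** No power, effect size or variance is given for AEC or percent, so there is no plan figure to reproduce beyond the pairwise level, 0.05/3 = 0.0167, which is right.

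**Inputs from the documents.** Twenty subjects per cohort; blood counts on days -7 and 4; a neutrophil fall reported or expected in the first week, which includes day 4; size of fall not given, except that "no subject in our studies with RV-16 has developed ANC's" below 1000 cells/mm³ (Section 1.3). No baseline eosinophil count is given for any cohort.

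**Assumed inputs.** Total white cells T = 6000 and neutrophils N = 3600 cells/mm³; neutrophil fall f of 20-50%. At 50%, neutrophils go to 3600 × 0.5 = 1800, which respects the bound above.

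**Step 1: the identity.** With eosinophils E unchanged, percent goes from 100·E/T to 100·E/(T − f·N). The relative rise is T/(T − f·N) − 1, the same for every E. The rise in points is the baseline percent times that factor.

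| Fall f | T − f·N | Relative rise | E = 300 (5.0%) becomes | E = 120 (2.0%) becomes |
|---|---|---|---|---|
| 20% | 5280 | 14% | 5.7% | 2.3% |
| 30% | 4920 | 22% | 6.1% | 2.4% |
| 40% | 4560 | 32% | 6.6% | 2.6% |
| 50% | 4200 | 43% | 7.1% | 2.9% |

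Two things follow. Every cohort whose neutrophils fall shows a rise. The rises differ between cohorts only if baseline percent or the fall differs. If neutrophils instead rose by 20%, T would be 6720 and 5.0% would become 300/6720 = 4.5%, so the sign reverses.

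**Step 2: effect on the planned three-group ANOVA at 0.05.** Simulated with no true eosinophil change, 20 per cohort and the same fall in all cohorts. AEC is log-normal (between-subject log SD 0.5, within-subject 0.2). Neutrophils are 3600 (log SD 0.25, within-subject 0.15) and other cells 2400.

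| Assumed geometric-mean AEC, asthma/AR/control | Percent ANOVA rejects, falls of 20% to 50% |
|---|---|
| Equal (200/200/200) | 4-5% throughout |
| 250/200/150 | about 7% to 19% |
| 300/250/120 | about 9% to 48% |

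With no fall, the percent ANOVA at 300/250/120 rejects in 5.4%, so the excess comes from the denominator. The ANOVA on the AEC change stays at about 5-6%.

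**Step 3: unequal falls.** At 300/250/120, with a 40% fall in controls and 20% in the allergic cohorts, the percent ANOVA rejects in about 6-7%, because the two differences nearly cancel. A separate set of assumptions (neutrophils 4000; AEC 150 in controls and 300 in the allergic cohorts; falls of 50% and 20%) reverses the gradient: +0.98 points in controls against +0.62 in the allergic cohorts.

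**Step 4: within-cohort change.** Under the Step 2 model, a test of the percent change against zero in the asthma cohort rejects in about 35% to 99% over falls of 20% to 50%. This does not need unequal baselines.

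**Step 5: could the fallback be triggered?** With log-normal eosinophils as assumed, a Shapiro-Wilk test on the residuals of the AEC change rejected normality in 61-79% of simulated trials. The plan names no such test, so this shows only that the fallback is a realistic branch.

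**The case against.** The strongest reply is that the fallback sentence is a copying slip. The heading, unit, model and null hypothesis of the AEC paragraph all concern AEC, the stray symbol matches the sentence that closes the next paragraph, and the neighbouring PD20 paragraph names its own variable correctly. That is probably so, and it is weak evidence of any intent to replace AEC. The rule is still wrong as written, and it governs a listed endpoint.

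A second reply is that the hypothesis does not rest on percent. AEC is analysed first, and a rise in percent beside a flat AEC would be visible. This stands for as long as the AEC analysis is run, and it limits the severity.

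A reader might infer more: that percent will show eosinophilia preferentially in the asthma and AR cohorts, and so reproduce the Section 13.1 prediction from neutropenia alone. The documents do not support that as a fact. It needs higher baseline eosinophils in those cohorts and a roughly similar neutrophil fall everywhere. Neither is given, and with equal baselines and equal falls the between-cohort test keeps its level.

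A reader might also take the 35-99% as the error rate of a planned test. The percent paragraph specifies no within-cohort test. Section 13.6 plans such tests for each primary and secondary outcome variable, but percent is not a listed outcome. Section 13.4.4 also covers other outcomes, so whether Section 13.6 reaches percent is unclear.

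Finally, the direction is not settled within the protocol. Section 1.1 cites neutrophilia. Lymphopenia is expected in Section 12.2.1 but infrequent in Section 12.2.3. The group's own RV-16 experience and the safety sections favour a neutrophil fall. A rise would bias percent downward and could mask a true eosinophil increase, so percent depends on its denominator in either case.

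**Conclusion.** The point holds and is minor. What is certain from the text is that the AEC fallback names the wrong variable; if followed, it leaves the listed endpoint without a usable test. It is certain by arithmetic that percent shifts when neutrophils shift and eosinophils do not, so the within-cohort change in percent is biased whatever the baselines.

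The size of any between-cohort error is not determined by the documents. It runs from none (4-5%, equal baselines and equal falls) to large (up to about 48%, for AEC 300/250/120 and a 50% fall). These rates rest on assumed baselines, variances and falls, and apply to the ANOVA on percent.

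**What to change.** 1. In the AEC paragraph of Section 13.4.4, replace the percent symbol in the alternative analysis with the change in AEC, so that the permutation test is run on the endpoint itself.
2. Keep the change in AEC as the tested blood-eosinophil endpoint.
3. Report the change in percent as descriptive or supportive only, beside total white cells and ANC for the same days, and state that the Section 13.6 within-group tests do not extend to it.
4. Reconcile Section 1.1 with Sections 1.3, 5.1, 12.2.1 and 12.2.3 on the expected direction of neutrophil change, and Section 12.2.1 with 12.2.3 on how often lymphopenia is expected.

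The cost is wording. The counts come from the CBC and differential already planned at Visit 1 and day 4. What is lost is one redundant test of an unlisted measure.

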### 3. Study Design

#### 3.1. Description of Study Design

A total of 60 subjects will be enrolled in this open label challenge study over a period of 48-54 months (September 2016 – March 2021). These will include 20 subjects in each of 3 cohorts: healthy controls, allergic rhinitis controls, and asthmatics. At Visit 1 subjects will have baseline assessments of lung function and blood work. Viral inoculation will be performed on day 0 and assessments of cold and allergy symptoms, nasal viral titers, nasal mediators, lung function, and FeNO will be obtained on days 0 and days 1, 2, 3, 4, and 7 post-infection (dpi). In addition, methacholine challenges (days -7 and 4) will be performed. Finally, nasal biopsies will be performed on day 4 to assess extent of viral infection and nature of cell death (apoptosis v. necrosis). Each subject will complete the study at day 14.

Table I: Study Outline\*\*\*

Visit #:	1	2	3	4	5	6	7	8	9
	Day -7	Day 0	Day 1	Day 2	Day 3	Day 4	Day 7	Day 14**	Day 21
Symptom Assessment	X	X	X	X	X	X	X	X	X
Negative CoVID19 screen (afebrile/preserved sense of smell)	X	X	X	X	X	X	X	X	X
Pregnancy Test	X	X				X	X		
Viral antibody serology/CBC	X								
Virus inoculation		X							
Viral titers		X	X	X	X	X	X		
FEV1/ FeNO	X	X	X	X	X	X	X	X	
Nasal Scraping		X	X	X	X	X	X		
Nasal Washes / Sponge		X	X	X	X	X	X		
Nasal Biopsy						X			
Blood for Th immune deviation / AEC	X					X			
Methacholine Challenge	X					X			

\*\*\* If subject is still symptomatic at day 14 they will be contacted at day 21 with the possibility of an unscheduled visit. A Day 21 in-person visit will be scheduled if ANC or ALC falls below 500/ $\mu$ L, and does not return to baseline following the Day 14 blood draw. If disease activity increases after day 7 or other concerns arise either between visits 6 and 7 or after visit 8, participants will be instructed to contact study personnel and may be asked to return to the study site for an "unscheduled" visit.

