
**Analysis of nasal biopsy samples:** Post-challenge day 4 nasal biopsy samples will be evaluated for % of infected cells and amongst the cells whether they display evidence of apoptosis (annexin V positive) or necrosis (PI positive). ***Analytic approach:*** Since the underlying distributions of these cell characteristics are complicated, we will use *distribution-free* permutation tests to conduct the *between-group* comparisons. ***Hypothesis testing:*** Based on the pseudo permutation test null distribution, a Bonferroni corrected two-sided  $p \leq 0.05/3$  decision rule will be utilized as the null hypothesis rejection rule for the *between-group* comparisons.

***Bivariate correlation analyses:*** As secondary analyses, we intend to examine bivariate relationships between several of the outcome variables. As one example, we intend to examine bivariate relationships between post-challenge day 0 to day 4 cumulative RV load and post-challenge day 3 and post-challenge day 4 expression of Th2 immune deviating activity (IL-25, IL-33 and TSLP). As a second example, we intend to examine bivariate relationships between post-challenge day 0 to day 4 post challenge cumulative RV load and post-challenge day 1, 2, 3, and day 4 innate expression of anti-immunity (IFN- $\alpha$ ,  $\beta$ ,  $\lambda$  and IL-15). Bivariate associations will be quantitatively expressed in terms of the non-parametric Spearman Rank correlation coefficient. Since multiple hypotheses will be tested, Bonferroni type I error rate corrections will be implemented in establishing the null hypothesis rejection rules.

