#### 13.6 Statistical Hypotheses

All of the hypotheses related to the primary and secondary outcomes will be two-sided. Three types of hypothesis tests will be conducted. The underlying motivation of one set of hypotheses (*between-group comparisons*) will be to examine if the distributions of the outcome random variable in the underlying study populations of the 3 study groups share the same location parameter value (e.g. mean, geometric mean). The underlying motivation of a second set of hypotheses (*within-group comparisons*) will be to examine if the underlying distributions of the outcome random variable pre- and post- RV challenge share the same location parameter value, and the underlying motivation of a third set of hypotheses (*bivariate-correlation*) will be to examine if the bivariate correlation between two random outcome variables is zero.

*Between-group comparisons*: With regard to the *between-group* comparisons, for each primary and secondary outcome variable the central *null hypothesis* is that the location parameter values (i.e. means or geometric means) of underlying distributions of the 3 study populations (i.e. asthmatics, allergic rhinitis controls, healthy-controls) are the same, whereas the *alternative hypothesis* is that at the underlying distributions of the 3 study populations have location parameter values that are not the same.

*Within-group comparisons*: With regard to the *within-group* comparisons, for each primary and secondary outcome variable the *null hypothesis* is that the underlying value of distribution location parameter (i.e. means or geometric means) is the same before and after RV-challenge, whereas the *alternative hypothesis* is that the underlying value of the distribution location parameter is not the same before and after RV-challenge.

*Bivariate-correlation*: With regard to bivariate correlation, the *null hypothesis* is that the underlying correlation between the two outcome random variables is zero, whereas the *alternative hypothesis* is that the underlying correlation between the two outcome random variables is non-zero.

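### The planned Spearman correlations have no cohort term and no stated analysis population; if the three cohorts are pooled, they can show an association that exists within none of them

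*Combined protocol and SAP*

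**What the plan says.** The bivariate correlation paragraph of section 13.4.4 gives two examples. The first relates cumulative RV load over days 0 to 4 to IL-25, IL-33 and TSLP on days 3 and 4. The second relates the same load to "post-challenge day 1, 2, 3, and day 4 innate expression of anti-immunity", meaning IFN-α, -β, -λ and IL-15. On method it says "Bivariate associations will be quantitatively expressed in terms of the non-parametric Spearman Rank correlation coefficient". On multiplicity it says that "Bonferroni type I error rate corrections will be implemented in establishing the null hypothesis rejection rules", without giving the number of tests.

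Section 13.6 describes the aim as to "examine if the bivariate correlation between two random outcome variables is zero". The null hypothesis "is that the underlying correlation between the two outcome random variables is zero", and "All of the hypotheses related to the primary and secondary outcomes will be two-sided". Cohort is not mentioned in either place.

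On design, section 3.1 says "These will include 20 subjects in each of 3 cohorts: healthy controls, allergic rhinitis controls, and asthmatics". Section 2.2 expects asthma and AR, but not controls, to show raised IL-25 (primary objective 1). It also expects more severe infection in asthma and AR than in controls (primary objective 3) and raised IL-33 and TSLP in those two cohorts (secondary objective 2). Secondary objective 6 asks whether greater severity in the asthma and AR cohorts goes with weaker innate immunity. Secondary outcome 6 in section 3.2 is itself worded as a correlation.

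**The concern.** When cohorts differ on both variables, cohort acts as a common cause. Subjects from asthma and AR tend to rank high on viral load and also high on the type 2 cytokines (or low on interferons, if those fall). The pooled ranks then correlate even if, within each cohort, a subject with more virus has no more cytokine than any other. A pooled coefficient would in part restate the between-cohort differences that the mixed models in sections 13.4.2 and 13.4.4 already test.

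The result most exposed is secondary objective 6. These correlations are the only analysis in section 13.4.4 that links viral load to the innate markers, so a cohort difference could be reported as a subject-level link between severity and innate immunity.

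**Working it through.** **1. Reproduce the plan's detectable differences (section 13.7).** The inputs are 20 per group, a two-sided two-sample t-test, alpha 0.05/3 = 0.0167 and power 0.80. The noncentral t gives a detectable standardised difference of 1.0636.
- RV load, SD 1.32: 10^(1.0636 × 1.32) = 25.35, against 25 stated. Power at 25 is 0.796.
- IL-25, SD 0.12: exp(1.0636 × 0.12) = 1.136, against 1.14 stated. Power at 1.14 is 0.823.

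Both figures reproduce. The stated factors as standardised shifts are:
- RV load: log10(25)/1.32 = 1.398/1.32 = 1.06 SD.
- IL-25: ln(1.14)/0.12 = 0.1310/0.12 = 1.09 SD.

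**2. Expected pooled correlation with none inside any cohort.** Two of the three equal cohorts are shifted, so the between-cohort share is (2/3)(1/3) = 2/9. For unit within-cohort variances the pooled product-moment correlation is

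(2/9)·d1·d2 / √[(1 + (2/9)d1²)(1 + (2/9)d2²)].

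With d1 = 1.059 and d2 = 1.092 this is 0.257 / √(1.249 × 1.265) = 0.257/1.257 = 0.20. The simulated mean Spearman coefficient agrees.

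**3. Simulated per-test rejection rates.** Each setting uses three cohorts of 20, normal data, zero correlation within every cohort and 20,000 trials. The thresholds take the Bonferroni family as 6 (3 cytokines × 2 days) or 16 (4 markers × 4 days). Both counts are assumptions built from the plan's examples.

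| Shift from controls | Mean rho | 0.05 | 0.05/6 | 0.05/16 |
|---|---|---|---|---|
| None | 0.00 | 4.9% | 0.9% | 0.4% |
| RV load only, 1.06 SD | 0.00 | 5.0% | 0.8% | 0.3% |
| Both variables, 0.5 SD | 0.05 | 7% | 1.3% | 0.6% |
| Both, half the design shifts | 0.06 | 7.2% | 1.6% | 0.7% |
| RV load 1.06 SD in asthma and AR; second variable in asthma only | 0.10 | 12% | 3% | 1.3% |
| Both, AR shifted half as far as asthma | 0.16 | 23% | 7.6% | 4.0% |
| Both at the design shifts | 0.20 | 35% | 14% | 8% |
| Design shifts, second variable downward | −0.20 | 35% | 14% | 8% |
| Both, 1.5 times the design shifts | 0.37 | 86% | 64% | 50% |
| Both, twice the design shifts | 0.51 | 99.5% | 97% | 93% |

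If both examples form one family of 22, the rate at the design shifts is 6.5%.

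**4. Why Bonferroni does not remove it.** The coefficient is centred away from zero, so a stricter threshold lowers the rate but not in proportion. At the design shifts, 0.348/0.05 is 7 times nominal, 0.138/0.0083 is about 17 times and 0.079/0.0031 is about 25 times.

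**5. After adjustment.** Ranking within cohort gives 5.0%, 0.9% and 0.3% at the design shifts and holds at 5.0% (0.05 level) at twice those shifts. A partial Spearman correlation (pooled ranks adjusted for cohort) gives 5.1%, 0.9% and 0.4% at the design shifts, and 5.9% at the 0.05 level at twice those shifts.

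**The case against.** The strongest reply is that pooling is not written down. Secondary objective 6 is framed for asthma and AR. Section 4.1 expects AR to respond just as asthma does, so correlating within those two cohorts alone would carry no cohort shift. That is fair. However, section 13.4.4 does not restrict the correlations in this way, and the equivalence of AR and asthma is an idea the trial sets out to validate. Elsewhere the plan says so when it means one cohort or each cohort, as for albuterol use and the within-group tests. If pooling is not intended, the population for a tested hypothesis is undefined, and similar wording is needed.

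Second, the null in section 13.6 is a zero correlation between two outcomes. In a pooled population with cohort shifts that null is false, so rejecting it is not strictly a type I error. This stands as a matter of definition. The rates above are false positives for the within-cohort question, which is the one of mechanistic interest. The separate mixed models would let a reader see the cohort differences, but would not remove them from the coefficient.

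Third, a detectable difference is not an expected one, and the plan gives no effect size for IL-33, TSLP, the interferons or IL-15. This also stands, and is why smaller shifts are shown. For the innate markers, section 1.1 describes a defective response in asthmatics. A deficit in AR relative to controls is an extension, not a stated hypothesis. The row with the second variable shifted in asthma only covers that case.

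**Conclusion.** The concern holds in a limited form. The plan tests plain bivariate correlations with neither a cohort term nor a named population. If the 60 subjects are pooled and cohorts differ on both variables, the coefficient can be significant with no association inside any cohort. At the plan's own detectable differences that happens in about 35% of tests at 0.05 and roughly 7% to 14% after Bonferroni, depending on the assumed family size. These figures rest on normal data, equal shifts in asthma and AR, and the IL-25 shift applied to the other markers.

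A reader might infer that the correlations will show a spurious association. The figures do not support that: most tests at the design shifts are not significant, the excess is small at half those shifts, and there is none if only one variable differs. Nor do the documents state that the cohorts are pooled. No primary conclusion changes; the affected results are secondary, chiefly secondary objective 6.

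**What to change.** In section 13.4.4, state the population for each correlation. Make the tested quantity a cohort-stratified Spearman correlation (rank within cohort, then combine over the three) or a partial Spearman correlation adjusted for cohort. The within-cohort ranking held its level better when shifts were large. Report the three cohort-specific coefficients with confidence intervals, and keep any pooled coefficient descriptive. Word the null in section 13.6 to match, as no association within cohorts, and give the number of tests in the Bonferroni family.

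The cost is SAP wording and two degrees of freedom (56 rather than 58 residual). No new data or subjects are needed, and the method remains valid if the cohorts turn out not to differ.
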